Hu14.18-IL2, an immunocytokine (IC) referred to as EMD 273063 by EMD Serono, Inc., Rockland, MA, formerly by EMD Pharmaceuticals, Inc., Durham, NC, consists of the humanized 14.18 (hu14.18) monoclonal antibody (mAb) genetically linked to 2 molecules of human recombinant interleukin-2 (IL2). Hu14.18-IL2 recognizes the disialoganglioside GD2, found on melanoma cells. IL2 has been tested extensively in melanoma clinical trials and is approved as an immune activator with documented antitumor effects in patients with melanoma. The chimeric (ch) form of the hu14.18 antibody (ch14.18) has been tested as an investigational therapeutic agent in Phase I clinical trials, alone and combined with other treatments including IL2, with antitumor effects demonstrated in these studies. Preclinical studies performed *in vitro* with human cells, *in vivo* in SCID mice bearing human tumor xenografts, and *in vivo* in immunocompetent mice bearing syngeneic tumor cells transfected to express the GD2 molecule, suggest that hu14.18-IL2 may have a greater antitumor effect than either IL2, hu14.18, or a combined regimen that includes both molecules. Results in tumor bearing mice treated with this molecule and other similarly configured molecules document that the most striking antitumor effects are obtained when the tumor burden is quite low. Initial trial results of hu14.18-IL2 in subjects with GD2⁺ tumors documented that hu14.18-IL2 is clinically safe and well-tolerated at doses that induce immunologic activation. However, despite this immunologic activation, no clear evidence of measurable antitumor effect was seen in our recent Phase I trial of hu14.18-IL2 for adults with melanoma (i.e., no subjects showed any complete or partial antitumor responses). Of 5 subjects treated in the Phase I trial with no evidence of disease at the time of treatment, 2 of these 5 subjects (treated at 0.8 and 6.0 mg/m²/day) continue with no evidence of disease (69-102 months). The other 3 recurred 2, 6 and 92 months after starting hu14.18-IL2 treatment. A separate Phase II study, using this same regimen, at a dose of 6 mg/m²/d, was recently completed. Fourteen patients with measurable disease were entered. Treatment was well-tolerated, with no protocol-defined DLTs. Of the fourteen subjects enrolled and treated in the Phase II trial, there was one confirmed partial response by RECIST criteria. Based on these initial preclinical and clinical data, this pilot protocol has been designed to evaluate the effect of 3 courses of hu14.18-IL2 treatment on the melanoma, the immune system, and the time to tumor progression for a small cohort of subjects with recurrent Stage III or Stage IV melanoma and “completely” resectable disease.

Cilengitide is an antivasular therapeutic that has been shown in animal models to have antiangiogenic effects, and is currently in clinical testing. Of great interest is the striking synergy that has been shown when cilengitide was added to treatment with ch14.18-IL2 in tumor bearing mice. Antitumor effects were noted against primary tumors, as well as against experimental and spontaneous metastases.

Initially, this protocol was designed to evaluate the effect of hu14.18-IL2 and of cilengitide, alone and in combination, for patients with Stage III or Stage IV melanoma thought to have completely resectable disease. The protocol was approved and opened in the spring of 2008, with subjects randomized to one of 4 arms. Subjects were further divided into those individuals needing extensive surgical versus non-extensive surgical procedures to achieve disease resection. Four subjects were enrolled and treated prior to the current (Version 5) protocol amendment.

UPDATE FOR PROTOCOL VERSION 5 (1/6/09)

Based on toxicities seen in one patient who received both cilengitide alone (cycle 1) and hu14.18-IL2 in combination with cilengitide (cycle 2), the decision was made to amend this protocol and to proceed using only hu14.18-IL2. The rationale for this decision, as well as the description of this serious adverse event, is described below in Section 5.4.5. All sections of the protocol that are not pertinent to subjects being enrolled following this amendment have been removed. The 4 subjects enrolled in this clinical study prior to this protocol amendment, three of whom received the combination therapy, were

monitored and managed as outlined in version 4 of the protocol. The statistical considerations section of the protocol, section 9, has been amended so that it pertains to the analysis plan following this amendment (2 treatment arms rather than 4 treatment arms) and provides the complete analysis plan for the revised protocol using hu14.18-IL2 alone, without administration of cilengitide.

SCHEMA

Treatment groups:

At the time of study entry, subjects will be randomized to Group A or B. Subjects in both groups will receive 3 cycles of immunocytokine (IC) therapy. Immunocytokine therapy will be given on days 1, 2, and 3 of each 28-day treatment course. Subjects randomized to Group A will undergo surgical resection of all sites of known disease following the first course of treatment. Subjects randomized to Group B will undergo surgical resection of all sites of known disease prior to the first course of treatment. This treatment schema allows for evaluation of the biological effects on the tumor of one cycle of Hu14.18-IL2 therapy.

SURGICAL RESECTION FOR GROUP A

(Course 1 of protocol therapy prior to surgery):

[figure not shown]
Subjects randomized to **Group A** will have complete surgical resection of all detectable melanoma following Course 1 of protocol therapy. Surgical resection will be scheduled for 7-14 days following the completion of the first course of treatment (i.e., days 10-17) in order to insure reversal of toxicities prior to the surgery. Once the subject has recovered from the surgery (2-4 weeks, depending upon the nature of the surgery), the subject will begin Course 2 of treatment. Initiation of course 2 will not be sooner than 4 weeks (29 days) after day 1 of the first course of study therapy. A total of 3 courses of protocol therapy are planned.

SURGICAL RESECTION FOR GROUP B

(Surgery prior to Course 1 of therapy):

Subjects randomized to **Group B** will have complete surgical resection of all detectable melanoma upon study entry, prior to Course 1 of protocol therapy. Once the subject has recovered from the surgery (2-4 weeks, depending upon the nature of surgery), the subject will begin Course 1 of hu14.18-IL2 treatment. A total of 3 courses of protocol therapy are planned.

A summary of the treatment groups and how they differ is shown:

Study agent administration:

TREATMENT COURSE ¹										
WEEK	1							2	3	4
DAY	1	2	3	4	5	6	7	8-14	15-21	22-28
Hu14.18-IL2 ²	X	X	X							

¹ All subjects will be scheduled to receive a total of 3 courses of treatment. Treatment will be stopped if it can not be tolerated or if there is recurrent disease.

² Hu14.18-IL2 will be administered as a 4-hour IV infusion on days 1, 2, and 3 in the first week of each treatment cycle. Each treatment cycle is 4 weeks (+/- 7 days). Subjects in this study will be administered 6 mg/m²/d of hu14.18-IL2, a dose corresponding to one dose below the maximal tolerated dose (MTD) as determined in our completed Phase I study.

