Surgery for recurrent stage III or stage IV melanoma can provide effective palliation for patients with isolated metastases as well as for patients with a limited number of metastases (76-78). In addition, some of these patients achieve long term benefit following surgery. Median survival for patients with melanoma metastatic to a distant site is less than 12 months (76). Prognostic features are identified in the current staging system, with 1-year survival rates ranging from 59 % for patients with metastases to skin, subcutaneous tissue, or distant lymph nodes (M1a disease), to 57 % for patients with metastases to the lung (M1b disease), to 41 % for patients with metastases to other visceral sites or with an elevated LDH (M1c disease) (79, 80). Beneficial results following complete surgical resection of distant metastases have been reported from several different institutions and demonstrate median survivals that depend on the site of the resected metastases (76). The median survival reported from several institutions following resection of skin or subcutaneous disease (17 months to 31 months) is better than the median survival following resection of metastases to the lung (9 months to 19 months) or following resection of nonhepatic gastrointestinal metastases (8 months to 18 months) (76, 81-93). There is a wide range in median disease-free survival following resection of metastatic lesions, with one series reporting a median disease-free interval of 8 months (range 0.6-91.8 months) following complete metastasectomy for an initial recurrence of stage IV melanoma (77). In addition, prolonged disease-free and long-term overall survival has been reported for patients who have a second lymph node dissection after isolated nodal recurrence and recurrent stage III disease (81). However, most of these metastatic melanoma patients still die from melanoma (76). An intergroup trial (E4697; SWOG E4697; CALGB 500101) with a planned sample size of 540 eligible subjects was designed to evaluate adjuvant therapy with GM-CSF or peptide vaccination in this subject population following surgical resection of metastatic disease and is currently in progress (“A Randomized, Placebo-Controlled Phase III Trial of Yeast Derived GM-CSF Versus Peptide Vaccination Versus GM-CSF Plus Peptide Vaccination Versus Placebo in Patients with ‘No Evidence of Disease’ after Complete Resection of ‘Locally Advanced’ and/or Stage IV Melanoma”). The subject eligibility for this large intergroup study includes subjects with completely resected disease with one of the following: a) any locoregional recurrence after prior adjuvant interferon or failure on S0008; b) any local recurrence of disease after adequate surgical excision of the original primary; c) mucosal melanoma; and d) stage IV melanoma (cutaneous, ocular, mucosal, or unknown primary). The initial estimate for this subject population was for a median overall survival of 15 months (personal communication; [name], study chair for E4697). The current pilot study will involve 16 subjects with completely resectable recurrent stage III or stage IV metastatic melanoma who have not yet received surgical resection of this disease.

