3.1 Inclusion criteria

3.1.1 Subjects must have recurrent stage III (i.e., recurrent regional metastasis), or stage IV (i.e., any distant metastasis) melanoma for which surgical resection would be clinically recommended, with biopsy proven (current or previous) Stage III or Stage IV disease. Any biopsies obtained to demonstrate recurrent regional metastasis or distant metastasis must be considered clinically appropriate for clinical management and must not be performed solely for meeting eligibility criteria. In addition, subjects must have disease that has not yet been completely excised and meets the following criteria:

3.1.1.1 Involves 3 or fewer sites. A nodal basin recurrence will be scored as one site, even if multiple nodes are positive. “Clustered” subcutaneous and/or cutaneous lesions that can be removed in a single surgical excision will be scored as one site, even if multiple subcutaneous and/or cutaneous lesions are present.

3.1.1.2 Subjects disease is determined to be completely resectable with uninvolved margins using standard surgical guidelines based on physical exam and radiographic imaging (MRI or CT of the head, and CT or MRI of the chest, abdomen and pelvis).

3.1.2 Subjects must have one of the following:

3.1.2.1 Stage III melanoma with recurrence after prior surgery, with or without subsequent adjuvant systemic (standard or experimental) and/or radiotherapy management.

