9.3.2 Sample Size/Accrual Rate

The first primary objective of this study is to evaluate the histological evidence of anti-tumor activity of hu14.18-IL2 by comparing pathological endpoints between the two groups after dichotomizing the evaluation of apoptosis, necrosis and cellular infiltrate into *positive* (i.e., the microscopic evaluation is classified as “low”, “medium”, or “high”) or *negative* (i.e., the evaluation is classified as “none”) using Fisher’s exact test. With eight subjects per group, a difference of 70% in the proportions of subjects classified as *positive* for necrosis, apoptosis, or cellular infiltrate between the two study arms will be detected with at least 82% power at a two-sided significance level of 0.1. A difference of 60% will be detected with at least 64%. Smaller differences are unlikely to be detected as statistically significant. The sample size chosen is sufficient to provide accuracy in the estimated rate of subjects classified as *positive*. Specifically, with eight subjects per group, the standard error of the proportions of subjects classified as *positive* necrosis, apoptosis, or cellular infiltrate for each group will be at most 0.18.

The second primary objective of this study is to evaluate the time to recurrence (duration of remission) and overall survival relative to historical control data described in Section 1.3.3. This study is not designed to detect differences in time to recurrence or overall survival between the two study arms. Instead, time to recurrence and overall survival time of both arms combined will be compared to historical controls qualitatively. Time to recurrence and overall survival time will be summarized using point estimates of the median time to recurrence/overall survival time and associated 90% confidence intervals. Furthermore, the two-year recurrence free survival rate and the two-year survival rate will be reported along with the corresponding 90% confidence intervals. The following table gives (two-sided) Wilson’s score 90% confidence intervals for the two-year survival/two-year recurrent-free survival rates, assuming a total sample size of 16 subjects.

Table 9: Ninety percent confidence bounds for two-year survival/two-year recurrent-free survival rates

Observed number of subjects alive/recurrent-free after 24 months	Proportions of subjects alive/recurrent-free after 24 months	Lower 90% confidence limit	Upper 90% confidence limit
2	0.12	0.04	0.32
4	0.25	0.12	0.45

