9.4.4 Primary Endpoints

Pathology evaluations of necrosis, apoptosis, and cellular infiltrate will be summarized in frequency tables (for each study arm). The proportions of subjects with tumor tissues classified as *positive* (i.e., the microscopic evaluation is classified as “low”, “medium”, or “high”) will be reported along with the corresponding 90% confidence intervals. The comparisons of pathology evaluations between the two study arms will be performed by Fisher’s exact test. For subjects in treatment group B, tumor tissues from biopsies obtained at study entry (pre-study biopsies) will be compared to surgically resected tumor tissues obtained after the first course of IC treatment. Paired comparisons of necrosis, apoptosis, and cellular infiltrate pathology evaluations will be performed using McNemar’s test.

Time to recurrence and overall survival will be summarized using point estimates of the median time to recurrence/overall survival and associated 90% confidence intervals. The data will be presented graphically using Kaplan-Meier plots. The two-year recurrence free survival rate and two-year survival rate will be reported along with the corresponding 90% confidence interval. Time to recurrence and overall survival will be contrasted to historical controls (47,49-53) as well as data from comparable subject groups being observed following surgically induced CR that may be published now and when the data from the present study are being analyzed.

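### Pooled recurrence and survival of recurrent stage III and stage IV subjects are contrasted with historical controls that depend on disease site, with no breakdown by stage or site, so case mix could be misread as drug effect

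*Combined protocol and SAP*

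**What the plan says.** Section 2.1.2 makes time to recurrence and overall survival a primary objective, and Section 9.2.1 lists both as primary endpoints. Both groups receive the drug (Section 5.3), so there is no untreated comparison for these outcomes.

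- **Population.** The Overview names among the aims "the time to tumor progression for a small cohort of subjects with recurrent Stage III or Stage IV melanoma". Section 3.1.1: "Subjects must have recurrent stage III (i.e., recurrent regional metastasis), or stage IV (i.e., any distant metastasis) melanoma". Section 3.1.2.2 admits stage IV disease from a cutaneous, ocular, mucosal or unknown primary, and Section 5.2.3 allows visceral disease.
- **Comparison.** Section 9.3.2: "time to recurrence and overall survival time of both arms combined will be compared to historical controls qualitatively". Section 9.4.4: "Time to recurrence and overall survival will be contrasted to historical controls (47,49-53) as well as data from comparable subject groups" published by the time of analysis.
- **Site dependence.** Section 1.5.3: "The median survival reported from several institutions following resection of skin or subcutaneous disease (17 months to 31 months) is better than" the figure for lung (9-19 months) or nonhepatic gastrointestinal metastases (8-18 months).
- **Stage III.** The same section says only that "prolonged disease-free and long-term overall survival has been reported for patients who have a second lymph node dissection after isolated nodal recurrence"; it gives no figure.
- **Other reference values in Section 1.5.3.** There is one disease-free figure, a median of 8 months from a stage IV metastasectomy series. There is one mixed-population survival figure, the 15-month planning estimate of an intergroup adjuvant trial, whose case-mix proportions are not given.
- **Handling of case mix.** Randomization is stratified by extent of surgery (Section 9.3.1). Section 9.4.2 summarises baseline variables and may use imbalances between arms as covariates in exploratory pathology analyses. Nothing in Section 9 breaks down or weights recurrence or survival by stage or site.

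**The concern.** The background section documents a prognostic factor, and the analysis then leaves it out of the only clinical benchmark. Stratifying by extent of surgery helps balance Group A against Group B. It does not align the pooled cohort with an outside series.

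A cohort with mostly skin or subcutaneous disease could look better than a general benchmark with an inert drug. One with mostly visceral disease could look worse and obscure a real effect. This matters because Section 9.1 asks whether activity is enough to warrant further evaluation, and Section 1.5.3 foresees a possible Phase III trial of the regimen.

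**Working it through.** **1. The plan's own figure.** Table 9 gives 90% Wilson limits for n = 16. With z = 1.645 and p = x/16, the limits are [p + z²/(2n) ± z·√(p(1−p)/n + z²/(4n²))] / (1 + z²/n). For x = 8 this gives 0.310 to 0.690, a width of 0.38. All seven rows and the stated maximum width of 38% reproduce.

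**2. How much of the spread is site** (medians from Section 1.5.3).
- Skin versus gastrointestinal: low ends 17/8 = 2.1; midpoints 24/13 = 1.8; high ends 31/18 = 1.7.
- Between institutions within one site: skin 31/17 = 1.8; lung 19/9 = 2.1; gastrointestinal 18/8 = 2.3.

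**3. Two-year survival implied by a median**, assuming exponential survival: S = 2^(−24/median).
- 8 months: 0.125; 9: 0.157; 13: 0.278; 14: 0.305; 15: 0.330
- 17: 0.376; 18: 0.397; 19: 0.417; 24: 0.500; 31: 0.585

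At midpoints, moving from all gastrointestinal to all skin shifts the rate by 0.500 − 0.278 = 22 points. That is less than the 38-point width of the widest interval.

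**4. Illustration against the 15-month benchmark (0.330).** The Wilson lower limit is 0.310 at 8/16 and 0.365 at 9/16, so the interval lies wholly above 0.330 with 9 or more alive. The upper limit is 0.316 at 2/16 and 0.388 at 3/16, so it lies wholly below with 2 or fewer alive. Binomial probabilities with an inert drug and complete two-year status:

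| True median or mix | Two-year survival | P(9 or more) | P(2 or fewer) |
|---|---|---|---|
| 8 months | 0.125 | <0.001 | 0.68 |
| 9 months | 0.157 | <0.001 | 0.53 |
| 15 months | 0.330 | 0.05 | 0.06 |
| Equal skin/lung/GI, midpoints 24/14/13 | (0.500 + 0.305 + 0.278)/3 = 0.361 | 0.08 | 0.04 |
| 17 months | 0.376 | 0.10 | 0.03 |
| 24 months | 0.500 | 0.40 | 0.002 |
| 31 months | 0.585 | 0.67 | <0.001 |

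The rows at 17, 24 and 31 months are the low end, middle and high end of the skin range, so each assumes that all 16 subjects have skin or subcutaneous disease. The 8-month row is the low end for gastrointestinal disease, and the 9-month row the low end for lung.

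**5. What a weighted benchmark would look like.** Expected number alive at two years = 16 × mean S.
- Equal mix, low ends: 16 × (0.376 + 0.157 + 0.125)/3 = 3.5. High ends: 16 × (0.585 + 0.417 + 0.397)/3 = 7.5.
- All skin: 16 × 0.376 = 6.0 to 16 × 0.585 = 9.4.

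The range moves with case mix, but it stays wide.

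**6. What cannot be computed.** The site medians are overall survival after resection of distant disease. The documents give no recurrence figures by site and no stage III figures, so the size of the shift is unknown for time to recurrence and for the stage III subjects.

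**7. The cited controls.** By their listed titles, references 47 and 49-53 are integrin or angiogenesis papers. Section 9.3.2 points to Section 1.3.3 for control data, but that section describes the function of the agent; the data are in Section 1.5.3.

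**The case against.** The strongest reply is that the plan does not claim what the illustration tests. Section 9.3.2 calls the contrast qualitative, and Section 1.5.4.5 calls it descriptive and expects a broad range. No section makes 15 months the reference or bases a claim on the Wilson limit. That stands: a reader might take the 40% and 67% as false-positive rates of the trial, and the documents do not support this. Both also need an all-skin cohort; the low end of the same range gives 10%, and an equal mix gives 8%.

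A reader might also set 31 months against 8 and infer a fourfold effect of site (31/8 = 3.9). That compares the best skin series with the worst gastrointestinal series and so mixes site with institution. Nor can the survival ratios be carried over to recurrence or to stage III.

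The 15-month estimate is a better match than its bare figure suggests. The intergroup trial's listed eligibility overlaps closely with Section 3.1.2, although its proportions are not given. Baseline variables will be summarised, and the extent-of-surgery stratum roughly separates thoracotomy and laparotomy cases from superficial disease. Neither is linked to the historical contrast.

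Finally, weighting leaves a wide benchmark, and four strata among 16 subjects average four each. This limits what the fix can deliver. It does not justify reporting only the pooled figure.

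**Conclusion.** The concern holds as a risk of interpretation. A primary objective rests on an informal contrast of about 16 pooled subjects with historical series. The protocol's own survival data differ about 1.7- to 2.1-fold between skin and gastrointestinal disease, and nothing in Section 9 shows or accounts for stage or site. Case mix could pass for benefit or failure.

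The illustrative chance of appearing to beat a 15-month benchmark with an inert drug runs from 5% at a true median of 15 months, through 8-10% for an equal mix or the low skin figure, to 40-67% for an all-skin cohort at the middle or top of its range. The chance of appearing to fall short is 53-68% at medians of 9 and 8 months. These figures assume exponential survival, the 15-month reference and known two-year status for all 16. The last is not guaranteed, since Section 9.3.2 sets minimum follow-up at 12 months after the last entry.

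The point merits a cheap improvement to the analysis section. It does not show that a planned test is invalid.

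**What to change.** In Section 9.4.4:

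1. List time to recurrence and overall survival separately for recurrent stage III and stage IV, and by site within stage IV.
2. Before outcomes are reviewed, name valid control series in place of references 47 and 49-53, and correct the pointer to Section 1.3.3 in Section 9.3.2.
3. Where stratum-specific survival figures exist, report observed against expected numbers alive at two years, weighted to the enrolled mix and shown as a low-high range. Do the same for recurrence only if published stratum figures are found.
4. State that the pooled figure alone will not be read as evidence of activity.

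The cost is about half a page and one table. Stage and site are already established for eligibility, so no extra subjects or visits are needed. The downside is that the benchmark becomes a wide range with few subjects per stratum, so the comparison stays descriptive.
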